# Postauthorisation Safety Study (PASS) Information

Acronym/title	FIRST-2.5: Finerenone Research of Early Safety and Effectiveness, Part 2.5
Protocol version and date	v 2.0, 03 JUL 2024
IMPACT study number	22663
Study type/study phase	Postapproval         ⊠ PASS       Joint PASS:       □ YES       ⊠ NO
EU PAS register number	Study not yet registered
NCT number	Study not yet registered

Active substance	Finerenone (BAY 94-8862) ATC code: C03DA05
Medicinal product	Kerendia
Product reference	EU/1/21/1616

Comparator/reference therapy	Patients with chronic kidney disease and type 2 diabetes not using finerenone
Study initiator and funder	Bayer AG, 51368 Leverkusen
Research question and objectives	This study addresses the research question of whether finerenone is effective and safe when used in real-world populations of adult patients with chronic kidney disease (CKD) and type 2 diabetes (T2D) in the United States compared with that in patients with CKD and T2D not using finerenone.
	
 
The primary objective in this study is the following:
 
To assess the effectiveness of finerenone by estimating the risk of a composite cardiovascular outcome (i.e., first occurrence of fatal or nonfatal acute myocardial infarction or hospitalisation for heart failure) in patients with CKD and T2D initiating finerenone compared with that in patients with CKD and T2D not using finerenone
 

The secondary objectives in this study are the following:
• To estimate the risk of the individual components of a composite cardiovascular outcome (i.e., first occurrence of fatal or nonfatal acute myocardial infarction; first occurrence of hospitalisation for heart failure) in patients with CKD and T2D initiating finerenone compared with that in patients with CKD and T2D not using finerenone (in the same primary study cohort as the primary analysis).
• To estimate the risk of new-onset heart failure (i.e., no previous history of heart failure) in patients with CKD and T2D initiating finerenone compared with that in patients with CKD and T2D not using finerenone (in a subset of the primary study cohort from which patients with a history of heart failure are excluded).
• To estimate the risk of a decline in urine albumin- creatine ratio (UACR) (i.e., first occurrence of specific UACR decline thresholds) in patients with CKD and T2D initiating finerenone compared with that in patients with CKD and T2D not using finerenone (in a subset of the primary study cohort of patients with baseline UACR values).
• To assess the safety of finerenone by estimating the risk of hyperkalaemia in patients with CKD and T2D initiating finerenone compared with that in patients with CKD and T2D not using finerenone
• To estimate the risk of the above mentioned outcomes in clinically relevant subgroups of patients with CKD and T2D initiating finerenone compared with that in patients with CKD and T2D not using finerenone
• To assess the effectiveness of initiating finerenone and titrating dosage according to the approved label by estimating the risk of outcomes of interest in patients with CKD and T2D initiating finerenone and uptitrating to 20 mg (when recommended) compared with that in patients with CKD and T2D not using finerenone
The exploratory objectives in this study are the following:
• To estimate the risk of all-cause mortality in patients with CKD and T2D initiating finerenone compared with that in patients with CKD and T2D not using finerenone
• To describe the change in UACR over time at 4 months and 12 months in patients with CKD and

	T2D initiating finerenone and in patients with CKD and T2D not using finerenone	
Country of study	United States	
Author	PPD	
	RTI Health Solutions	

## 2. List of abbreviations

ACEi	Angiotensin-converting Enzyme Inhibitors
ACEi/ARB	Angiotensin-converting Enzyme Inhibitors/Angiotensin Receptor Blockers
AMI	Acute Myocardial Infarction
ARB	Angiotensin Receptor Blockers
ATT	Average Treatment Effect in the Treated
CI	Confidence Interval
CKD	Chronic Kidney Disease
CONSORT	Consolidated Standards of Reporting Trials
COVID-19	Coronavirus Disease 2019
DALY	Disability-adjusted Life-year
DPP-4i	Dipeptidyl Peptidase-4 Inhibitor
eGFR	Estimated Glomerular Filtration Rate
EHR	Electronic Health Record
EMA	European Medicines Agency
ENCePP	European Network of Centres for Pharmacoepidemiology and Pharmacovigilance
ESKD	End-stage Kidney Disease
EU	European Union
FDA	Food and Drug Administration
FOUNTAIN	Finerenone Multidatabase Network Data Generation
GLP-1 RA	Glucagon-like Peptide-1 Receptor Agonists
GPP	Guidelines for Good Pharmacoepidemiology Practices
GVP	Good Pharmacovigilance Practices
HbA1c	Glycated Haemoglobin A1c
HR	Hazard Ratio
ICD-10-CM	International Classification of Diseases, Tenth Revision, Clinical Modification
IPC	Inverse Probability of Censoring
IRB	Institutional Review Board
MedDRA	Medical Dictionary for Regulatory Activities
MRA	Mineralocorticoid Receptor Antagonists
N/A	Not Applicable
NNH	Number Needed to Harm
nsMRA	Non-steroidal Mineralocorticoid Receptor Antagonists
OQ	Office of Quality

OS	Observational Study
PAS	Postauthorisation Study
PASS	Postauthorisation Safety Study
QC	Quality Control
QPPV	Qualified Person responsible for Pharmacovigilance
RR	Relative Risk
RTI	RTI International
RTI-HS	RTI Health Solutions
SAP	Statistical Analysis Plan
SGLT2i	Sodium-glucose Cotransporter 2 Inhibitors
sIPT	Stabilised Inverse Probability of Treatment
SOP	Standard Operating Procedure
STROBE	Strengthening the Reporting of Observational Studies in Epidemiology
T1D	Type 1 Diabetes
T2D	Type 2 Diabetes
UACR	Urine Albumin-Creatine Ratio
US	United States

#### Acronym/title FIRST-2.5: Finerenone Research of Early Safety and Effectiveness, Part 2.5 **Protocol version and date** 2.0, 03 JUL 2024 **IMPACT** study number 22663 Study type/Study phase Postapproval PASS Joint PASS: **YES** $\boxtimes$ NO Author PPD , FISPE, RTI Health Solutions **Rationale and** Finerenone is an oral, selective, non-steroidal background mineralocorticoid receptor antagonist for the treatment of chronic kidney disease (CKD) in patients with type 2 diabetes (T2D) in the United States (US) and other countries. This study will evaluate the effectiveness and safety of finerenone in real-world use in the US. **Research question and** This study will address the research question of whether objectives finerenone is effective and safe when used in real-world populations of adult patients in the US with CKD and T2D compared with that in patients with CKD and T2D not using finerenone. The primary objective is to assess the effectiveness of finerenone by estimating the risk of a composite cardiovascular outcome (i.e., first occurrence of fatal or nonfatal acute myocardial infarction or hospitalisation for heart failure) in patients with CKD and T2D initiating finerenone compared with that in patients with CKD and T2D not using finerenone.

### 4. Abstract

The secondary objectives in this study are the following:
• To estimate the risk of the individual components of a composite cardiovascular outcome (i.e., first occurrence of fatal or nonfatal acute myocardial infarction; first occurrence of hospitalisation for heart failure) in patients with CKD and T2D initiating finerenone compared with that in patients with CKD and T2D not using finerenone (in the same primary study cohort as the primary analysis).
• To estimate the risk of new-onset heart failure (i.e., no previous history of heart failure) in patients with CKD and T2D initiating finerenone compared with that in patients with CKD and T2D not using finerenone (in a subset of the primary study cohort from which patients with a history of heart failure are excluded).
• To estimate the risk of a decline in urine albumin- creatine ratio (UACR) (i.e., first occurrence of specific UACR decline thresholds) in patients with CKD and T2D initiating finerenone compared with that in patients with CKD and T2D not using finerenone (in a subset of the primary study cohort of patients with baseline UACR values)
• To assess the safety of finerenone by estimating the risk of hyperkalaemia in patients with CKD and T2D initiating finerenone compared with that in patients with CKD and T2D not using finerenone
• To estimate the risk of the above mentioned outcomes in clinically relevant subgroups of patients with CKD and T2D initiating finerenone compared with that in patients with CKD and T2D not using finerenone
• To assess the effectiveness of initiating finerenone and titrating dosage according to the approved label by estimating the risk of outcomes of interest in patients with CKD and T2D initiating finerenone and uptitrating to 20 mg (when recommended) compared with that in patients with CKD and T2D not using finerenone
The exploratory objectives in this study are the following:
• To estimate the risk of all-cause mortality in patients with CKD and T2D initiating finerenone compared with that in patients with CKD and T2D not using finerenone
• To describe the change in UACR over time at 4 months and 12 months in patients with CKD and

	T2D initiating finerenone and in patients with CKD and T2D not using finerenone	
Study design	This is a new user cohort study based in existing healthcare data of patients with CKD and T2D initiating finerenone and patients with CKD and T2D not using finerenone.	
Population	The study cohort will be composed of adults (aged $\geq 18$ years) with CKD and T2D who are eligible for finerenone prescription during the time period since finerenone became available in the US (beginning 09 July 2021). The study cohort will identify patients who initiate finerenone (Time 0 = finerenone initiation date) and a comparator group of individuals with CKD and T2D not using finerenone (Time 0 = all dates with a recorded diagnosis of CKD meeting the inclusion criteria).	
	For inclusion, patients will be required to have sufficient enrolment in the data source, have no previous use of finerenone, be aged 18 years or older, and fulfil algorithms for the diagnoses of T2D and CKD. Patients will be excluded if they have evidence of type 1 diabetes, end-stage kidney disease or kidney cancer, or contraindications to or conditions warning against treatment with finerenone (i.e., adrenal insufficiency, estimated glomerular filtration rate < 25 mL/min/1.73 m  , recent hyperkalaemia diagnosis or serum potassium > 5.0 mEq/L, use of a strong CYP3A4 inhibitor, pregnancy, or hepatic impairment).	
	Patients will be followed from Time 0 until occurrence of a study outcome or until the end of the study period, disenrollment from the data source, or deviation from their treatment strategy.	
Variables	Finerenone exposure will be evaluated using medication prescribing and dispensing records. Outcomes will be identified using recorded diagnoses or laboratory data. Patient characteristics will be evaluated with diagnosis, procedure, laboratory test result, and medication records.	
Data sources	This study will be conducted using existing healthcare data from the US. Considered data sources include the HealthVerity® Chronic Kidney Disease Masterset, which includes closed administrative healthcare claims, electronic medical records, and laboratory testing results. Additional data sources may be considered to increase the sample size or representativeness of the study sample. If multiple data sources are used, meta-analytic methods may be considered, as appropriate, to generate summary estimates across data sources.	

Study size	Sample size estimates suggest that there would be a greater than 80% probability of the 95% confidence interval of the relative risks to exclude 1 at total sample sizes of approximately 30,000 individuals (2,727 finerenone users, and the rest comparators) for the higher estimate of composite cardiovascular outcome incidence and 60,000 individuals (5,455 finerenone users) for the lower estimate of composite cardiovascular outcome incidence. For secondary effectiveness and safety outcomes with lower expected incidence, larger sample sizes would be required to achieve the same level of precision.
Data analysis	The characteristics of treated and untreated groups will be described. Incidence rates of outcomes by treatment group will be estimated, and the cumulative incidence over time will be plotted. Outcome occurrence in the treatment groups will be compared with the stabilised inverse probability of treatment-weighted hazard ratios and 95% confidence intervals. Time-specific risk ratios and risk differences will be estimated to describe potentially changing risk over time. Subgroup analyses will be performed, and sensitivity analyses and negative control outcomes will evaluate the impact of potential biases. A secondary objective evaluating a different treatment strategy of finerenone initiation and label-directed uptitration will also be evaluated.
Milestones	The data collection (i.e., start of data extraction for the secondary use of data) is expected to start 01 October 2024 and end 30 June 2025, with the final report of study results expected by 31 December 2025.

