The comparator group of patients with T2D and CKD untreated with finerenone will consist of all encounters during which an individual was recognised as having CKD and was eligible to be prescribed finerenone but was not. All calendar dates with an encounter with a recorded diagnosis of CKD will be considered as potential Time 0s. The selection criteria (Section 9.2.1.2) will be evaluated at every identified potential Time 0, and all Time 0s meeting the selection criteria will be included in the comparator group. Multiple comparator Time 0s per person may be eligible and selected (Figure 2), including dates for individuals who subsequently initiate finerenone (i.e., information on an individual's future prescription or dispensing for finerenone will not be used to define eligibility). Although this is difficult to confirm before conducting the analysis, the general assumption is that patients with CKD and T2D would visit a physician at least once per year. At each interaction, the physician could potentially recognise the patient as having CKD (i.e., record the diagnosis in the electronic health record [EHR]). When combining the above assumption with an estimated maximum study period of 3 years, we anticipate the number of potential Time 0s per individual in the comparator group to generally be less than 5.

T2D = type 2 diabetes.

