### 9.2.2. Study timeframe

The cohort entry period (the time period during which all Time 0s will be identified) will begin on 09 July 2021 (the date of FDA approval in the US) and will end at the latest available data in the data source at the time of analysis. Data from before 09 July 2021 will be used—and potentially back to 01 October 2015, as available—to define selection criteria, washout periods, and covariates.

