#### 9.3.4. Covariate definitions

Covariates include risk factors for renal progression [39,40], cardiovascular outcomes [41,42], or hyperkalaemia [43-45]. Variables potentially associated with the use or non-use of finerenone and the outcomes of interest—e.g., concomitant medications, comorbidities—will be identified for all cohort members before or on Time 0 using diagnosis, procedure, or medication information available in the data source. A detailed description of definitions and code lists for all covariates that will be used in the data source will be specified in the SAP. Covariates will be defined using ICD-10-CM diagnosis codes, laboratory records, procedure coding, or medication coding, as appropriate for each variable.

The following demographic characteristics will be evaluated as of Time 0:

- Age
- Sex
- Calendar year of Time 0
- Race and/or ethnicity (as available in the data)
- Socioeconomic status (as available in the data)
- US geographic region
- Insurance plan type

The following clinical characteristics of patients will be defined using the 365 days before and including Time 0, except where specified otherwise:

- Markers of T2D severity (as available in the data source) and components of the Diabetes Severity Complications Index [46,47] not listed elsewhere
  - Duration of T2D (in all available lookback, as available in the data source)
  - Insulin use
  - Haemoglobin A1c (glycated haemoglobin) (HbA1c) (most recent recorded laboratory value in the 183 days before and closest to Time 0, if available)
  - Hyperosmolar hyperglycaemic state
  - Ketoacidosis

- Lower limb amputations (all available lookback, as available in the data source)
- Neuropathy
- Retinopathy
- Markers of kidney dysfunction severity
  - Duration of CKD (all available lookback, as available in the data source)
  - CKD stage, defined based on eGFR, or stage-specific diagnosis codes (using all available lookback) (Section 9.3.1)
  - Albuminuria stage defined based on UACR values (Section 9.3.1)
  - Proteinuria, defined based on diagnosis codes (Section 9.3.1)
  - Nephrotic syndrome, based on diagnosis codes (Section 9.3.1)
  - Glomerulonephritis
  - Renovascular disease
  - Polycystic kidney disease
  - Autoimmune disease
  - Gout/hyperuricaemia
  - Hospitalisation episodes for acute kidney injury

The following comorbidities will be defined using all available lookback before and including Time 0:

- Cardiovascular comorbidities
  - Acute myocardial infarction

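### Calendar year is the only calendar-time covariate named, so if uptake rises within years users still enter a few weeks later than nonusers; the bias is small and a finer date term removes it almost free

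*Protocol*

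**What the plan says.** - **Entry window.** Protocol 9.2.2 has one entry period for both groups: it "will begin on 09 July 2021 (the date of FDA approval in the US) and will end at the latest available data". The abstract describes the same date as the start of availability, "during the time period since finerenone became available in the US (beginning 09 July 2021").
- **Comparator records.** Under 9.2.1, "All calendar dates with an encounter with a recorded diagnosis of CKD will be considered as potential Time 0s". Each qualifying date is one on which the patient "was recognised as having CKD and was eligible to be prescribed finerenone but was not". One person may contribute several, over "an estimated maximum study period of 3 years".
- **Calendar time.** The list in 9.3.4 contains "Calendar year of Time 0" and no finer date variable. The same section says that detailed "definitions and code lists for all covariates that will be used in the data source will be specified in the SAP".
- **Analysis.** Section 9.7.2 plans logistic propensity scores, stabilised weights and standardised differences, with refinement of the model if residual imbalance is seen. Section 9.7.3 runs follow-up on time since Time 0 and gives risk ratios and differences at 6, 12 and 18 months. No matching or risk-set sampling on date is planned, and calendar time is not among the limitations in 9.9.

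**The concern.** Uptake of a newly launched drug usually climbs, while encounters coded for kidney disease arrive fairly evenly. Within any calendar year the initiators would then cluster later than the comparator records. Weighting on year equalises the number of records per year in the two groups but not the dates within it.

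If cardiovascular admissions vary by season or drift over time, a shift of some weeks in entry date moves the outcome risk slightly for reasons unrelated to the drug. The 6-month risk ratio is the most exposed, because a 6-month window covers only part of a seasonal cycle. The refinement step in 9.7.2 responds to visible imbalance, and a balanced year row shows none.

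**Working it through.** **Plan's own figure.** The protocol gives no number on calendar time. Its precision statement in 9.5 (risk ratio 0.86, 10:1) reproduces. With a pooled two-proportion formula the probability is 83.2% at 30,000 records and 14.4% risk, and 80.2% at 60,000 and 7.2%. On the log risk ratio it is 81.2% and 78.4%. That calculation does not depend on this point.

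**Inputs.** From the protocol: entry from 09 July 2021, about 3 years of entry, 10:1, at least 20,000 users, estimates at 6 and 12 months. Assumed: entry ends about September 2024 (1,180 days), comparator records are uniform over time, and uptake, seasonality and drift are as listed below.

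**Step 1: residual shift in entry date.** Both groups were weighted exactly to the same calendar-year mix and the mean entry days compared.
- Linear uptake: 20 days. Linear after a 60-day gap: 25. Doubling every 6 months: 32. Quadratic: 35. Doubling every 3 months: 59.
- Linear, doubling per year or tripling per year, with first use 0 to 90 days after approval: 16 to 32 days.
- The crude shift under linear uptake, before any adjustment, is 197 days.
- After year weighting, the standardised difference of the entry date in the first set of curves is about 0.06 to 0.17. The year row shows 0.

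**Step 2: secular trend.** The approximate bias factor is (annual risk multiplier)^(shift/365.25). For a 10% annual decline:
- unadjusted, linear: 0.9^(197/365.25) = 0.945 (0.943 in the day-by-day model);
- year-adjusted, linear: 0.9^(20/365.25) = 0.994 (0.994 in the model).

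The bias falls from 5.7% to 0.6%, so year removes 1 − 0.6/5.7, or about 90%. Across the first set of curves the year-adjusted factor is 0.983 to 0.994; the 0.983 belongs to doubling every 3 months.

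**Step 3: seasonality plus drift, no drug effect.** Hazard = 5% per year × (1 + amplitude × cosine peaking in mid-January) × exp(drift × years). Uptake is linear, doubling or tripling per year; first use 0 to 90 days after approval; amplitude 10 to 20%; drift −10% to +10% per year.
- 6-month risk ratio: 0.998 to 1.027.
- 12-month risk ratio: 0.992 to 1.008, and 1.000 without drift, because a full year averages the season out.
- Hazard ratio to 18 months (first use 0 to 60 days): 0.995 to 1.011.

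**Step 4: scale against sampling error.** The 6-month risk is p = 1 − exp(−0.05 × 0.5) = 0.0247. SE of ln RR = √[(1 − p)/(20,000p) + (1 − p)/(200,000p)] = √(0.001975 + 0.000198) = 0.047, before any inflation from weighting. ln 1.027 = 0.027, or 0.57 SE.

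**Step 5: effect of a finer date term.** In the first set of curves, calendar quarter cuts the shift to 2.4 to 5.2 days and calendar month to 0.3 to 0.6 days. At a 10% annual decline the bias factor becomes 0.9985 to 0.9992 (quarter) or 0.9998 to 0.9999 (month). In the model of Step 3, month strata with a common start at first use give a 6-month risk ratio of 0.9997 to 1.0003.

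**The case against.** Much of the opposing case stands.

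- **Nothing in the protocol shows that users enter later.** It gives no uptake curve, outcome trend or seasonal pattern. A date shift biases the result only if risk or its recording changes within the year beyond what the other covariates carry.
- **Year adjustment does most of the work.** A reader might infer that calendar confounding remains intact in the risk ratios. The arithmetic does not support that. A 6-month risk ratio of 1.045 can be produced, but only with uptake tripling yearly, a 60-day lag, 40% winter amplitude and risk rising 10% per year together. Even then ln 1.045 = 0.044, just under one SE.
- **Drift is not wholly invisible.** Only the year row is blind to it. Drift carried by comedications, laboratory testing, COVID-19 diagnosis or vaccination would appear in those rows, and a negative control outcome is run before the primary analyses.
- **A positivity violation is not shown.** A reader might infer that comparator records exist from dates when nobody could be treated. The abstract, section 7 and 9.2.2 all give 09 July 2021, and nothing says the drug could not be prescribed from then. A pre-use period rests on an assumed lag; with none, there are no such records.
- **The SAP may define the variable more finely,** since covariate definitions are left to it.

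The last point does not remove the concern. The protocol names year as the covariate, and its trigger for refinement is visible imbalance, which the year row cannot supply for a shift within the year.

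**Conclusion.** The point holds as a low-severity, near-free improvement. If uptake rises after launch, year is too coarse to align entry dates, and users would enter about 15 to 60 days later after weighting. The resulting bias is about 0 to 3% in the 6-month risk ratio at 10 to 20% seasonality. It is about 1% or less at 12 months and in the hazard ratio for linear, yearly doubling or yearly tripling uptake. The steepest curve tried, doubling every 3 months, reaches 1.7% at a 10% annual trend. All of this is small beside the planning risk ratio of 0.86.

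The direction is not fixed: winter seasonality pushes the ratio above 1, while a falling outcome trend pushes it below 1. More records do not shrink the bias, which is the reason to remove it when doing so costs so little. Every size here depends on assumed uptake, season and drift, none of which the protocol reports.

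**What to change.** - **Section 9.3.4:** replace "Calendar year of Time 0" with calendar month or quarter, or a spline of the Time 0 date, and use it in the propensity model.
- **Section 9.7.2:** add the standardised difference of the Time 0 date, before and after weighting, to the balance table.
- **Section 9.2.2:** if the data show a gap between approval and the first observed finerenone use, start comparator entry at that first use, because earlier records have no treated counterpart.

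**Cost.** A few more model terms and one more table row. If there is a gap, some early comparator records are lost: 30/1,180 = 2.5% for a 30-day gap and 90/1,180 = 7.6% for a 90-day gap, with uniform comparator entry. These would be 30/176 = 17% and 90/176 = 51% of the 2021 comparator records. Section 9.5 expects far more comparators than the study needs, so the loss is affordable.
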